Skills Training to Enhance Vocational Outcomes in Veterans with Serious Mental Illness

July 10, 2020

NCT02663349

Background and Rationale: Schizophrenia and bipolar disorder are profoundly disabling illnesses. Only 15% and 24% of individuals with these conditions are competitively employed, as compared to nearly 70% of healthy individuals⁽¹⁾. Vocational rehabilitation programs such as supported employment have proliferated in recent years to facilitate work placement of individuals with serious mental illness. These programs have successfully placed individuals, typically doubling employment rates⁽²⁾. However, maintenance of employment is dependent upon being able to successfully integrate into one's work setting. This can present a significant challenge to individuals with serious mental illness, as they typically exhibit impairment in their ability to accurately perceive and understand social exchanges^(1, 3, 4). Thus, in addition to work skills, these individuals are also likely to need assistance developing skills to manage the social demands of work. To enhance vocational outcomes, integration of psychological interventions with vocational programs has been recommended⁽⁵⁾.

Social cognition is the ability to accurately perceive and understand the social world and encompasses emotion recognition, interpretation of social exchanges (Theory of Mind), and inference of motivations (Attribution Bias). Social cognitive deficits are associated with functional disability and have been found to be unique predictors of community⁽⁶⁻⁸⁾ and work functioning^(9, 10). The impact of social cognition on functional outcomes is direct and indirect. Bell and colleagues found that the relationship between social cognition and work performance was mediated by social discomfort, suggesting that difficulty understanding social interactions led to discomfort around co-workers, and ultimately, affected job performance⁽⁹⁾. Similarly, Brekke et al. noted that social cognition contributed to poor role functioning both directly and through social competence and perceived social support⁽⁷⁾. Individuals with poor social cognitive ability functioned less effectively because they were less able to respond skillfully in social interactions and to perceive and access support from others. Given its strength as a predictor and proximity to functioning, social cognition has become an intervention target⁽¹¹⁾.

Results of recent studies suggest that social cognitive abilities are modifiable in both schizophrenia⁽¹²⁾ and bipolar disorder⁽¹³⁾. Presently, the most established intervention is Social Cognitive Intervention Training (SCIT), a 12-week group intervention in which participants learn strategies to enhance emotion recognition and to assess the accuracy of their interpretation of social interactions⁽¹⁴⁾. SCIT's ultimate goal is for training to transfer beyond the social cognitive training targets to more distal outcomes such as enhanced role functioning. The first full scale clinical trial of SCIT's efficacy found that the impact of training generalized beyond social cognitive performance and resulted in increased skillfulness in social interactions⁽¹⁵⁾.

To enhance transfer of training gains to functional outcomes, two pilot studies have paired participants with a social mentor to facilitate completion of homework and to ensure that skills are practiced outside of treatment (supported SCIT). Both studies reported improvements not only in social cognition but also in social relatedness⁽¹⁶⁾ and community functioning⁽¹⁷⁾. The proposed study will extend this work by being the first to examine the impact of supported SCIT on work role functioning. When other types of skills training have been paired with work, a synergistic effect has been noted, with greater^(18, 19) and more sustained⁽²⁰⁾ treatment gains observed, presumably because work offered opportunities to practice skills.

Specific Aim 1: This study will assess the feasibility of providing supported SCIT to individuals with serious mental illness who are engaged in work activity or school (i.e., competitive employment, hospital based compensated work therapy placement, volunteer work, school). One 2-hour group-based skills training sessions will be offered weekly. The group training will be supplemented with individual sessions with a group co-facilitator to complete homework tailored to the work setting.

Hypothesis 1. Supported SCIT will be completed by 75% of enrolled veterans, a rate comparable to non-supported SCIT offered to non-veterans⁽²¹⁾. Completion will be defined as attendance at 80% or more of group and individual sessions.

Specific Aim 2: This study will assess the impact of supported SCIT on social cognitive intervention targets as well as functional outcomes.

Hypothesis 2. Recipients of supported SCIT are expected to demonstrate performance gains on measures of social cognition, perceived social support, social competence, social comfort, and work performance post-intervention.

Specific Aim 3: This study will assess durability of intervention-induced change.

Hypothesis 3: Recipients of supported SCIT are expected to sustain gains in social cognitive and functional domains during a 3-month follow-up period.

Methods:

Study Design. An open-trial pilot study will be conducted in which participants attend 12 weeks of supported SCIT.

Participant Inclusion/Exclusion Criteria. Participants will be individuals, ages 18-70, with a DSM-5 diagnosis of schizophrenia, schizoaffective disorder, or bipolar disorder who are engaged in work activity. In addition, participants must be clinically stable, defined as no psychiatric hospitalizations and no changes in antipsychotic or mood stabilizing medication in the 4 weeks prior to study enrollment, and participants must be able to participate appropriately in a group-based activity, as judged by no recent history of disruptive behavior in groups and no history of unprovoked aggression toward others. Participants will be excluded if they have met criteria for substance abuse in the last month or substance dependence in the last 6 months, if they are not fluent enough in English to understand testing procedures, if they have premorbid IQ less than 70, or if they do not have the capacity to give informed consent.

Participant Recruitment. Patients will be recruited from the Minneapolis VAHCS. A study investigator or a Master's level study staff person will meet with mental health staff to provide information about the study and to request that information be provided to appropriate patients. We will also post advertisements describing the study at the VAHCS. In addition, with a waiver of consent for screening and a waiver of HIPAA authorization for screening purposes, the investigators will request a list of patients treated at the Minneapolis VAHCS who have a chart diagnosis and are within the age of participants eligible for this study. These individuals will be sent an IRB-approved letter that describes the study and that offers them the opportunity to indicate whether they would like to hear more about the study. Participants who do not respond to research staff within two weeks of receipt of the letter will receive a follow up phone call from research staff asking them if they would like additional information about the study. When a prospective participant expresses interest in the study, research staff will further describe the study to him/her. If the participant continues to be interested, a brief eligibility screening will take place. If the participant appears to be appropriate, the participant will be asked to provide consent for a diagnostic interview. If the potential participant appears appropriate for the study, he or she will be given the opportunity to complete the protocol and provided with a consent form. The consent form will contain a detailed description of all study procedures, as well as possible risks and benefits. [name], another study investigator, or a Master's level study staff member will review the content of the form with the participant and respond to any questions or concerns. To ensure comprehension of the information provided in the informed consent forms, participants will be asked to answer questions about the information on the consent form. Indicators that a participant cannot currently comprehend meaningfully the content of the consent form will include: 1) the potential participant has severe formal thought disorder that does not allow him or her to ask understandable questions or to paraphrase the basic points in the consent form; 2) the potential

participant is unable to maintain attention to the description of the consent form long enough to perceive the individual basic points in the consent form; 3) the potential participant cannot ask questions or respond sufficiently to indicate agreement due to catatonia; or 4) the potential participant expresses delusions related to the research protocol that significantly distort his or her basic understanding of the research. In contrast, some indicators that the potential participant can provide meaningful consent will include: 1) ability to pay attention well enough to read the form or have it read and described to him/her; 2) ability to paraphrase the basic points in the consent form; and 3) ability to ask reasonable questions about the research and associated treatment conditions.

Study Intervention. The intervention will consist of one 2-hour, small group training session and 30-minutes of individualized supported practice of skills with a treatment facilitator weekly. [name] and bachelor and master's level assistants will offer the intervention. The Social Cognitive Intervention Training (SCIT) will be described as a relationship skills class. The class will consist of a combination of lecture, demonstrations, and role-play activities. Participants will learn skills to facilitate emotion recognition. They will also learn strategies to assist with perspective taking and assessing the accuracy of attributions about social situations.

Assessment. See Table 1 for all assessment measures. Participant diagnosis will be established with a SCID diagnostic interview. In addition, to establish eligibility, structured interviews will be conducted to obtain participant demographics, medical, and psychiatric history. In addition, the Wechsler Test of Adult Reading will be administered to obtain an estimate of pre-morbid IQ. Baseline, post-intervention (3-month), and follow up (6-month) assessments will measure social cognitive training targets, functional outcomes, and potentially confounding variables such as symptom severity with instruments previously used with this patient population. Social cognitive domains will be assessed with the Bell-Lysaker Emotion Recognition Task, the Ambiguous Intentions and Hostility Scale, the Facial Emotion Identification Test, and The Awareness of Social Inference Task. Social competence, community functioning, perceived social support at work, and social comfort at work, will be assessed with the Social Skills Performance Assessment, the Mentoring and Communication Support Scale, the First Episode Social Functioning Scale, the Vocational Efficacy in Trauma Survivors Scale, and the Mentoring and Communication Support Scale. Potential confounds, symptom severity and outside treatment hours, will be assessed with the Brief Psychiatric Rating Scale and the treatment update interview.

Statistical Analysis: Descriptive statistics, including means, standard deviations, and measures of frequency will be used to describe the sample as well as uptake and engagement in treatment. Repeated measure ANOVAs and paired sample t-tests will be used to test for the effects of Time on social cognitive and functional outcome variables. Magnitude of within group change with treatment will be measured with Cohen's d.

References

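### Hypothesis 1 predicts 75% completion, but only a frequency is planned, so the Aim 1 conclusion makes no allowance for sampling error

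*Combined protocol and SAP*

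**What the plan says.** Specific Aim 1 is to assess the feasibility of supported SCIT. Under it, Hypothesis 1 states that "Supported SCIT will be completed by 75% of enrolled veterans" and supports the figure as "a rate comparable to non-supported SCIT offered to non-veterans". The endpoint is defined per participant: "Completion will be defined as attendance at 80% or more of group and individual sessions". So 75% is the rate the investigators expect, and it is the only benchmark in the text.

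The design is a single-arm pilot: "An open-trial pilot study will be conducted in which participants attend 12 weeks of supported SCIT".

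For Aim 1 the Statistical Analysis offers descriptive statistics, under which "measures of frequency will be used to describe the sample as well as uptake and engagement in treatment". The inferential methods it names serve other aims: "Repeated measure ANOVAs and paired sample t-tests will be used to test for the effects of Time" on the social cognitive and functional variables. For completion, the plan gives no confidence interval, no test, no lower acceptable rate and no rule for calling the hypothesis supported. It also gives no planned number of participants.

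**The concern.** Feasibility is the first aim, and a single-arm pilot can address it more directly than efficacy. The hypothesis carries a number, so readers will ask whether it was reached. The only tool the plan supplies is a comparison of one percentage with another.

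In a small sample that comparison is unstable. When the benchmark equals the expected rate, an observed rate below it is a common result even if the expectation is exactly right. An observed rate at or above it can also arise from a clearly lower true rate. The risk is that Aim 1 is reported as confirmed or refuted on a difference of one participant.

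**Working it through.** **Inputs.** The hypothesised rate of 75% and the denominator (all enrolled) come from Hypothesis 1. The number enrolled is not stated, so n = 12, 20 and 30 are assumptions, chosen as plausible for a pilot. The plan has no figure of its own to reproduce.

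**Step 1: chance of falling short when the hypothesis is exactly true.** Assume the hypothesis is read as met when observed completion is at least 75%. Let r be the smallest whole number not below 0.75n. The chance of falling short at true rate p is P(X ≤ r − 1), with X binomial(n, p). The chance of reaching 75% is 1 minus this.

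| Assumed n | r | Falls short, true 75% | Reaches 75%, true 60% |
|---|---|---|---|
| 12 | 9 | 1 − 0.649 = 0.351 | 0.225 |
| 20 | 15 | 1 − 0.617 = 0.383 | 0.126 |
| 30 | 23 | 1 − 0.514 = 0.486 | 0.044 |

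Over n = 10 to 60, the chance of reaching 75% at a true 75% runs from 0.455 (n = 11) to 0.649 (n = 12). At n = 100 it is 0.553. A larger sample makes a pass at a true 60% less likely, but it does not stop a programme that is exactly on target from falling short often.

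**Step 2: precision around the benchmark.** The exact (Clopper-Pearson) 95% limits for x completers are the 0.025 quantile of Beta(x, n − x + 1) and the 0.975 quantile of Beta(x + 1, n − x).

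- 9/12 (75%): 42.8% to 94.5%
- 15/20 (75%): 50.9% to 91.3%
- 14/20 (70%): 45.7% to 88.1%

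The two n = 20 results fall on opposite sides of 75%, yet their intervals almost coincide. Wilson limits give the same picture: 53.1% to 88.8% for 15/20 and 48.1% to 85.5% for 14/20.

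**Step 3: what wording from the interval would do.** Call completion below the hypothesised rate only if the exact upper limit is under 75%. The largest x that satisfies this is 5 of 12 (upper limit 72.3%), 10 of 20 (72.8%) and 17 of 30 (74.5%). The chance of that statement is P(X ≤ x):

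| Assumed n | Largest x | True 75% | True 60% |
|---|---|---|---|
| 12 | 5 | 0.014 | 0.158 |
| 20 | 10 | 0.014 | 0.245 |
| 30 | 17 | 0.022 | 0.422 |

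Wrongly reporting a shortfall at a true 75% drops from 35% to 49% down to about 1% to 2%. The last column shows the limit of the approach: at a true 60%, most results would still be compatible with 75%. Compatibility is therefore not confirmation, and the lower limit has to be reported with it.

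**The case against.** The strongest reply is that the plan never sets a pass mark. Hypothesis 1 is a prediction, its basis is a comparable rate (which may mean an approximate one), and the Statistical Analysis promises only to describe engagement. No progression decision or stopping rule depends on the result, and anyone given x and n can compute the interval. Much of this stands. The at-least-75% rule in the working is a reading of the text, every probability depends on an assumed n, and the consequence is confined to how Aim 1 is reported. What remains is that a numbered hypothesis invites a conclusion and the plan provides no precision with which to draw one. A purely descriptive proportion from a small sample also needs an interval.

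A reader might infer two stronger points that the documents do not support:

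- *That the feasibility verdict is a coin toss.* No verdict rule is written. Under the inferred rule, a true 75% programme reaches the mark with probability 0.649 at n = 12 and 0.617 at n = 20. Only n = 30, at 0.514, is near one half.
- *That the plan should adopt a floor, such as 50%, and a three-way verdict of feasible, inconclusive or not met.* No floor appears in the documents. Requiring an exact lower limit above 50% leaves the mark at 15/20 for n = 20. At n = 12 the mark becomes 10/12, which cuts the chance of a feasible verdict at a true 75% from 0.649 to 0.391. At n = 30 it becomes 21/30, which raises that chance at a true 60% from 0.044 to 0.176. Any minimum acceptable rate is for the investigators to set.

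**Conclusion.** The concern holds as a gap in precision and wording. With frequencies alone, Aim 1 would rest on a point estimate compared with 75% and no allowance for sampling error. If *met* means observed completion of at least 75%, a programme with a true 75% rate falls short about 35% to 49% of the time at n = 12, 20 or 30, and at n = 20 one participant separates two results that are statistically indistinguishable. These sizes rest on the assumed n, on that reading of the hypothesis, and on independent participants with a common completion rate. The gap does not invalidate the study. It affects what Aim 1 can conclude, and it is nearly free to close.

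**What to change.** Add to the Statistical Analysis:

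1. Completion will be reported as the number and percentage of all enrolled participants, with an exact (Clopper-Pearson) or Wilson 95% interval. Name one of the two in advance, since they can differ at small n.
2. The Hypothesis 1 conclusion will be worded from that interval. Completion is below the hypothesised rate only if the upper limit is under 75%. Otherwise the data are compatible with 75%, and the lower limit is reported as the lowest completion rate they support. A point estimate just above or below 75% will not be treated as confirming or refuting the hypothesis.

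If the investigators want a minimum acceptable rate, they should set and justify it themselves. One chosen after the data are seen should be labelled as such.

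The cost is about two sentences and no new data, and the change can still be made at the reporting stage. The downside is a less definite feasibility statement: in a small sample many results will be compatible with 75% and also with considerably lower rates.

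### Does the 80% completion rule need to say whether group and individual sessions are pooled or counted separately?

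*Combined protocol and SAP*

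**What the plan says.** Hypothesis 1, under Specific Aim 1, sets the target: "Supported SCIT will be completed by 75% of enrolled veterans". The next sentence gives the rule for a single participant: "Completion will be defined as attendance at 80% or more of group and individual sessions".

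The schedule is spread over three places. Specific Aim 1 gives the frequency of the group component ("One 2-hour group-based skills training sessions will be offered weekly") and mentions the individual component without a frequency ("The group training will be supplemented with individual sessions with a group co-facilitator to complete homework tailored to the work setting"). Study Design gives the duration: "participants attend 12 weeks of supported SCIT". Study Intervention gives the weekly content of both components: "one 2-hour, small group training session and 30-minutes of individualized supported practice of skills with a treatment facilitator weekly".

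The Statistical Analysis paragraph does not restate the completion rule. Its plan for this outcome is descriptive: means, standard deviations and "measures of frequency will be used to describe the sample as well as uptake and engagement in treatment".

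**The concern.** Completion is the only criterion named for Aim 1, and 75% is the only numerical target in the three hypotheses. A rule with two readings therefore sits under the main feasibility figure. The per-type reading is the stricter one, so if the choice were left until attendance was known, the more favourable rate could be reported.

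The readings also answer somewhat different questions. The individual sessions are what make this the supported form of SCIT. Under pooling, a participant can miss a third of the individual sessions and still count as a completer. In a small pilot, one or two such participants could move the reported rate across 75%.

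The plan also never prints a total number of sessions, so the denominators seem to be missing as well.

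**Working it through.** The plan prints no session total, sample size or expected attendance, so it has no figure to reproduce. The check derives the denominators, compares the two rules, and then sees how far the rates could differ.

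**Denominators.** Study Design gives 12 weeks. Study Intervention gives one group session and 30 minutes of individual practice per week. If the weekly 30 minutes is one session:

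- group: 12 × 1 = 12
- individual: 12 × 1 = 12
- total: 24

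The denominators therefore follow from the plan. All that is open is whether the 30 minutes is always a single session and how cancelled or make-up sessions count.

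**Cut-offs.**

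- Pooled: 0.80 × 24 = 19.2, so at least 20 of 24.
- Per type: 0.80 × 12 = 9.6, so at least 10 of 12 group and at least 10 of 12 individual.

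Since 10 + 10 = 20, every per-type completer is also a pooled completer. Six attendance patterns (group, individual) pass only under pooling: (12, 8), (12, 9), (11, 9), (9, 11), (9, 12) and (8, 12).

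**Size of the difference (assumed scenarios).** Give each participant one attendance probability p, shared by both session types, with p ~ Beta(a, b). Let g and i be sessions attended out of 12. Pooled completion is P(g + i ≥ 20) and per-type completion is P(g ≥ 10 and i ≥ 10). A smaller a + b means attendance is closer to all-or-none.

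| Mean attendance | a + b | Pooled | Per type | Gap (points) |
|---|---|---|---|---|
| 85% | 0.5 | 78.6% | 77.2% | 1.4 |
| 85% | 1 | 75.2% | 72.8% | 2.4 |
| 85% | 2 | 71.8% | 67.9% | 3.9 |
| 85% | 5 | 68.8% | 62.1% | 6.7 |
| 85% | 10 | 68.1% | 58.9% | 9.1 |
| 90% | 0.5 | 85.5% | 84.5% | 1.0 |
| 90% | 1 | 83.3% | 81.5% | 1.8 |
| 90% | 2 | 81.3% | 78.3% | 3.0 |
| 90% | 5 | 80.7% | 75.4% | 5.2 |
| 90% | 10 | 82.1% | 74.9% | 7.2 |

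(Gaps are taken before rounding.) In a sample of 20, a gap of 1.0 to 9.1 points is 20 × 0.010 = 0.2 to 20 × 0.091 = 1.8 participants.

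**Chance that the readings fall on opposite sides of 75%.** Classify each participant as a per-type completer, a pooled-only completer or neither. With k = 15 for N = 20 and k = 30 for N = 40, the chance is P(per-type count < k and pooled count ≥ k).

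| Mean attendance | N | a + b = 0.5 | 1 | 2 | 5 | 10 |
|---|---|---|---|---|---|---|
| 85% | 20 | 5% | 10% | 15% | 20% | 24% |
| 85% | 40 | 7% | 14% | 19% | 19% | 20% |
| 90% | 20 | 2% | 5% | 10% | 19% | 25% |
| 90% | 40 | 1% | 5% | 12% | 26% | 33% |

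At mean attendance of 80% or 95% the chance is below 9% in every case. Across these scenarios it therefore runs from near zero to about a third, depending on inputs that the plan does not supply.

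**What depends on the result.** The plan attaches no test, confidence limit, alpha or progression rule to the 75%. The completion rule does not enter the repeated-measures ANOVAs, the paired t-tests or Cohen's d for Aims 2 and 3.

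**The case for a change.** The strongest case for a change is that the ambiguity is real, concerns the Aim 1 outcome, and would take one sentence to remove. The scenarios above also treat the two session types alike, which may understate the difference. With independent attendance of 0.95 per group session and 0.80 per individual session (assumed values), 83.2% complete under pooling and 54.7% per type, on opposite sides of the target. Settling the reading after attendance is seen would be poor practice.

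Most of that stands as description. The sentence has two readings, nothing else in the plan resolves them, and the choice can change whether the reported rate reaches 75%. The complaint about denominators largely falls away, because 12 weeks of weekly sessions gives 12 and 12.

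What does not stand is the step to a change in the plan. Neither reading is wrong, and naming one would not improve the method. No decision is tied to the result, so crossing 75% alters only how the pilot is described. The planned description of engagement has room for attendance by session type, and a reader given that can see what either reading implies. The large gap under unequal attendance would itself show up in such a description.

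**Conclusion.** No change is called for. The completion rule leaves out one detail, whether 80% is pooled (20 of 24) or per type (10 of 12 of each), and a competent analyst fills it by naming the reading used and describing group and individual attendance separately. Both readings give a valid descriptive rate, and no decision depends on which is used.

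If the two session types are attended equally well, at 85% to 90% on average, the rates differ by about 1 to 9 points, or at most about two participants in 20. They fall on opposite sides of 75% in about 1% to 33% of samples of 20 or 40. The difference could be larger if attendance differs by type. These figures rest on 12 group and 12 individual sessions, one individual session per week, and assumed attendance, spread between participants and sample sizes, because the plan gives none of the last three. They bound a reporting ambiguity and do not show an error in the plan.

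### Training is given in small groups but the planned tests treat participants as independent; if change is correlated within groups, p-values for gains from baseline will be too favourable, and no check is planned

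*Combined protocol and SAP*

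**What the plan says.** Study Design describes a single-arm study: "An open-trial pilot study will be conducted in which participants attend 12 weeks of supported SCIT". Under Study Intervention, "The intervention will consist of one 2-hour, small group training session" is combined with "30-minutes of individualized supported practice of skills with a treatment facilitator weekly". The same section says of the sessions: "The class will consist of a combination of lecture, demonstrations, and role-play activities". More than one member of staff delivers them: besides the lead, "bachelor and master's level assistants will offer the intervention". Specific Aim 1 links the individual component to the group: "The group training will be supplemented with individual sessions with a group co-facilitator".

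Statistical Analysis names one inferential approach: "Repeated measure ANOVAs and paired sample t-tests will be used to test for the effects of Time on social cognitive and functional outcome variables". It adds descriptive statistics, and Cohen's d for the size of within-group change.

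The document does not state the sample size, the number or size of training groups, how participants are assigned to groups or facilitators, or a significance level. It does not mention a group or facilitator term, an ICC, cluster-robust errors, or recording which group a participant attended.

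**The concern.** A paired t-test or repeated-measures ANOVA allows for correlation between one person's measurements over time. It does not allow for correlation between people. Here members of a training group share a leader, peers and role-plays for 12 weeks, and the individual practice is with a group co-facilitator. Several outcomes (emotion recognition, social inference, social competence) are close to the skills practised in that room. It is plausible that a good group improves together and a poor group stalls together.

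If so, the participants carry less independent information about mean change than their number suggests, and a test that counts them as independent rejects too often. There is no control arm, so these tests and Cohen's d are the only quantitative evidence planned for Aims 2 and 3. One unusual group could drive a significant result, and nothing in the planned output would show it. If group membership is never recorded, the question may be impossible to examine later.

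**Working it through.** The plan has no sample-size, power or ICC figure to reproduce, so this is an illustration.

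**Inputs**
- From the document: small-group delivery, a single arm, and paired t-tests or repeated-measures ANOVAs for Time.
- Assumed: a two-sided 5% level; each participant stays in one group; group size m of 4, 6 or 8; number of groups k of 3 or 4; ICC of change scores within a group from 0 to 0.20.

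**Step 1: variance of mean change.** With equal groups, the design effect is DE = 1 + (m − 1) × ICC, and the true standard error is √DE times the naive one. At m = 6:
- ICC 0.05: DE = 1 + 5 × 0.05 = 1.25; √1.25 = 1.118, so the true standard error is about 12% larger.
- ICC 0.10: DE = 1.50; √1.50 = 1.225, about 22% larger.
- ICC 0.20: DE = 2.00; √2.00 = 1.414, about 41% larger.

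**Step 2: true type I error of a nominal 5% test.** In the normal approximation this is 2 × [1 − Φ(1.96/√DE)]. For m = 6 and ICC 0.10: 1.96/1.225 = 1.60, giving 0.110.

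| ICC | m = 4 | m = 6 | m = 8 |
|---|---|---|---|
| 0 | 5.0% | 5.0% | 5.0% |
| 0.02 | 5.7% | 6.2% | 6.6% |
| 0.05 | 6.8% | 8.0% | 9.2% |
| 0.10 | 8.6% | 11.0% | 13.3% |
| 0.20 | 12.1% | 16.6% | 20.6% |

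Simulating the paired t-test with 4 groups of 6 (24 participants) gives about 5%, 6%, 8%, 11% and 17% down the same ICC column, so the approximation is adequate.

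**Step 3: effect on a borderline result.** By the same approximation, a naive p of 0.03 corresponds to about 0.052 at DE 1.25, 0.076 at DE 1.5 and 0.125 at DE 2.0, before any loss of degrees of freedom.

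**Step 4: does a valid alternative exist?** A t-test on the k group means, with k − 1 degrees of freedom, held its simulated type I error at about 5% in every scenario run (k of 3, 4 or 6; ICC 0 to 0.20). A random group effect on change with small-sample degrees of freedom gave 3.0%, 3.9%, 4.7% and 5.5% at ICC 0, 0.05, 0.10 and 0.20 with 4 groups of 6.

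**Step 5: what it costs.** Take a true change of 0.6 SD and no clustering.
- 4 groups of 6: the noncentrality is 0.6 × √24 = 2.94. Power is 80% for the paired t-test (23 df), 52% for the group-means test (3 df) and about 55% for the random-effect analysis.
- 3 groups of 6: the noncentrality is 0.6 × √18 = 2.55. Power is 67% for the paired t-test (17 df) against 31% for the group-means test (2 df).

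**The case against.** The strongest case against the point has four parts.

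**The bias is conditional.** A reader might infer that the planned standard errors are too small as a matter of fact. The document does not support that. It gives no ICC; at 0 there is no inflation and at 0.02 it is slight. Part of the training is one-to-one, with homework tailored to each person's work or school setting, which could lower the correlation on work outcomes. This objection stands, and the point is worded accordingly. It does not justify taking the ICC as exactly zero without a check, as the planned tests do.

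**The direction does not carry over to all of Aim 3.** A reader might infer that every test of durability is too favourable. Hypothesis 3 is that gains last through follow-up. If that is judged by finding no significant decline from 3 to 6 months, a standard error that is too small makes a decline easier to declare, which works against the hypothesis. The plan does not say which contrast is used, so the direction is shown only for tests against baseline.

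**Little formal weight rests on these tests.** The plan states no confidence intervals, power figure or success rule, the feasibility aim is untouched, and without a control arm even a well-calibrated p-value cannot attribute change to training. All of this is true and limits the importance of the point. It does not remove it, because Hypotheses 2 and 3 are directional and the plan tests them.

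**Adjustment can be costly.** One might go further and ask that conclusions rest only on a group-adjusted analysis. The power figures above argue against that when the number of groups is unknown, and with a single group no adjustment is possible. This also stands, and it limits the remedy to a sensitivity analysis.

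**Conclusion.** The point holds in conditional form. Delivery is grouped, the only inferential methods assume independent participants, and nothing in the plan would detect or allow for clustering. If the ICC of change within groups is positive, p-values for change from baseline to 3 months, and for any test from baseline to 6 months, are too favourable. For 4 groups of 6 the true type I error of a nominal 5% test would run from about 6% to 17% over ICCs of 0.02 to 0.20. Group number, group size and ICC are all assumptions; smaller groups or a lower ICC shrink the problem and larger ones increase it. Estimates of mean change remain unbiased. In an uncontrolled pilot the practical weight is moderate, but the remedy is cheap enough to be worth making.

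**What to change.** In Statistical Analysis:

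1. Record each participant's training group.
2. Report the number and size of groups and the mean change in each.
3. Beside each planned test of change, give a group-adjusted 95% confidence interval as a prespecified sensitivity analysis. Use either a random group effect on change (a group-by-time effect) with Satterthwaite or Kenward-Roger degrees of freedom, or a t-test on group means. A random group intercept on raw scores is not enough, because it cancels in the pre-post difference.
4. Where the planned and adjusted results disagree, describe the gain as not robust to clustering.
5. If there is only one group, state that clustering cannot be estimated.

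The cost is one recorded variable and one extra analysis per outcome, with no new participants or assessments. The downside is imprecision. In the 4-groups-of-6 illustration with no clustering, power of 80% against 52% for the group-means test means that the two tests disagree in at least 80 − 52 = 28% of trials with a true 0.6-SD change, purely from lost degrees of freedom. The report should say this when it describes a disagreement, and the adjusted interval should stand beside the planned analysis rather than replace it.
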